2. STUDY DESIGN

2.1. Synopsis of Study Design

This is a multisite trial to evaluate the efficacy and safety of GWP42003-P in patients with IS who have failed to become spasm- and hypsarrhythmia-free following treatment with 1 or more approved IS therapies (e.g., steroids and/or VGB). All approved therapies must be discussed with the patient's parent(s)/legal representative before the patient is considered for the trial (discussions regarding treatment options must be documented). The trial will comprise of a pilot safety phase, followed by a pivotal phase, with a 1 year OLE extension available to all patients who complete either phase. The pilot phase will be open-label with 2 sequential cohorts of 5 patients, the first cohort aged between 6 and 24 months and the second cohort aged between 1 and 24 months, who will receive GWP42003-P for 2 weeks. The pivotal phase will comprise 192 patients, aged 1–24 months, who will undergo a 2-week, randomized, placebo-controlled, double-blind treatment period.

An independent DSMC will be used throughout the study; they will consider safety of the patients, and will confirm doses and dose regimens to be investigated in the pivotal phase, as well as the plans for dose titration. If required, following DSMC review, adjustment of doses and dose regimens will also take place following the first cohort of 5 patients in the pilot phase.

Patients will enter the pilot and pivotal phases at the respective screening visits (Visit 1, Day -7 to -1) for assessment of eligibility, which includes a prolonged video-EEG. Patients who satisfy all eligibility criteria will then be administered GWP42003-P (pilot phase) or randomized to GWP42003-P (1 of 2 dose levels) or placebo at a 1:1:1 ratio (pivotal phase) (Visit 2, Day 1 [+3 days]). The High Dose Level will be as recommended by the DSMC; the Low Dose Level will be defined as 50% of the High Dose Level. Patients in the placebo group will be split into 2 equivalent cohorts: half receiving Low Dose Level dosing volumes and half receiving High Dose Level dosing volumes. Following baseline assessments, patients will titrate the investigational medicinal product (IMP) in 10 mg/kg/day increments to the target dose level (or equivalent volume of placebo in the pivotal phase) and will continue at this dose, or the highest tolerated dose up to 40 mg/kg/day, for the remainder of the 2-week treatment phase. Patients in the pilot phase will remain in the clinic as inpatients during the 4-day dose titration period. If deemed safe by the DSMC then it is planned for those in the pivotal phase to titrate in an outpatient setting. Further clinic-based assessments will take place after 3 days' dosing (Visit 3, Day 4 [+1 day]). All patients in the pilot and pivotal phases will return to the clinic after 2 weeks' dosing (Visit 4, Day 15 [+3 days]) or earlier if they withdraw prematurely. All patients who complete treatment will then have the opportunity to receive GWP42003-P during the subsequent OLE phase. The OLE phase will last for a maximum of 1 year.

Patients who enter the OLE phase will remain on the same dose (pilot phase) or will transition to their target dose of GWP42003-P over 4 days in a blinded manner (pivotal phase). Patients may continue at this dose, or the highest tolerated dose up to 40 mg/kg/day, for the remainder of the OLE phase. GWP42003-P may be discontinued at the discretion of the investigator. During the OLE phase, clinic visits will take place on Day 19 (Visit 5 [+1 day]), Day 29 (Visit 6 [±3 days]), Day 43 (Visit 7 [±3 days]), Day 71 (Visit 8 [±3 days]), Day 127 (Visit 9 [±7 days]), Day 211

(Visit 10 [±7 days]), and on Day 295 (Visit 11 [±7 days]). Patients will return to the site for an end of OLE treatment visit on Day 379 (Visit 12 [±7 days]) or earlier if they withdraw prematurely from the OLE phase. Following end of treatment, withdrawal, or discontinuation of IMP, all patients will taper the IMP over 10 days followed by safety follow-up. Patient diaries will be completed each day by the caregiver during the trial.

2.2. Randomization Methodology

The pilot and OLE phases of this study are single-arm and open-label with no randomization. After confirmation of eligibility at Visit 2, all patients are assigned GWP42003-P in the pilot phase and continue on this same treatment in the OLE phase.

2.3. Stopping Rules and Unblinding

The patient must be withdrawn from the trial if ANY of the following apply:

- Any issue with eligibility criteria that is considered to potentially compromise the safety of the patient.
- Administrative decision by the investigator, GW, or regulatory authority.
- Protocol deviation that is considered to potentially compromise the safety of the patient.
- Withdrawal of the patient's parent(s)/legal representative consent.
- QTcB of 500 msec or greater on ECG, or a shift from baseline QTcB of 60 msec or greater.
- Lost to follow-up.
- ALT or AST $> 3 \times$ ULN with the appearance of fatigue, nausea, vomiting, right upper quadrant pain or tenderness, fever, rash, and/or eosinophilia (> 5%).
- ALT or AST $> 8 \times ULN$.
- ALT or AST $> 5 \times$ ULN for more than 2 weeks.

ALT or AST $> 3 \times$ ULN and (TBL $> 2 \times$ ULN or INR > 1.5). The patient may also be withdrawn from the trial for ANY of the following:

- Any other issue with eligibility criteria (non-safety related).
- Any requirement to increase the dose of concomitant AED(s) or to add in new AED(s) during the pilot or pivotal phase.
- If a patient is not showing evidence of benefit during the OLE phase (the option of withdrawing from the trial will be discussed with the caregiver at each visit).
- Patient/caregiver non-compliance.
- AE (including clinically significant laboratory result) which, in the opinion of the investigator, would compromise the continued safe participation of the patient in the trial.

There is no blinding necessary for the pilot and OLE phases so unblinding procedures will not apply.

2.4. Study Procedures

The schedule of assessments, as outlined in the study protocol, is provided in **Table 1**.

 Table 1
 Schedule of Assessments

		Pilot or Pi	votal phase		Open-Label Extension Phase									
Visit Number Day (Visit Window)	Visit 1 Day -7 to -1	Visit 2 ¹ Day 1 (+3 days)	Visit 3 Day 4 (+1 day)	Visit 4 ² Day 15 (+3 days)	Visit 5 Day 19 (+1 day)	Visit 6 Day 29 (±3 days)	Visit 7 Day 43 (±3 days)	Visit 8 Day 71 (±3 days)	Visit 9 Day 127 (±7 days)	Visit 10 Day 211 (±7 days)	Visit 11 Day 295 (±7 days)	Visit 12 Day 379 (±7 days)	End of Taper Period Visit ³ (+3 days)	Safety Follow-up Visit ⁴ (+3 days)
Informed consent	X													
Patient number	X													
Eligibility criteria	X	X ⁵												
Start of IMP dosing		X												
Inpatient stay (pilot phase only)		X	X											
Demographics	X													
Medical history	X													
Concomitant medication review	X	X	X	X	X	X	X	X	X	X	X	X	X	X
Physical examination	X	X		X		X	X	X	X	X	X	X	X	

Vital signs	X	X	X	X	X	X	X	X	X	X	X	X	X	
ECG	X	X^6	X^7	X^7	X	X	X	X	X	X	X	X	X	
Video-EEG (8-24 hours)	X			X		X	X		X	X	X	X		
Clinical laboratory sampling (blood/urine)	X		X	Х	X	X	X	X	X	X	Х	X	X	
AEs	X	X	X	X	X	X	X	X	X	X	X	X	X	X
PK blood sampling ⁸		X		X	X									
Caregiver paper diary issue/training	X													
CGIC		X ⁹		X		X	X	X	X	X	Х	X		
PGIC		X ⁹		X		X	X	X	X	X	X	X		
Vineland-II		X								X		X		
IMP dispensing ¹⁰		X		X		X	Х	Х	X	X	X			
IMP compliance review				X		X	X	Х	X	X	X	X	X	
Caregiver diary review		Х	X	X	X	Х	X	X	X	X	Х	X	X	X
Spasm/seizure information		Х	X	X	X	X	X	Х	X	X	X	X	X	X

IMP usage ¹¹		X	X	X	X	X	X	X	X	Х	X	X	
Changes in concomitant AEDs	X	X	X	X	X	X	X	X	X	X	X	X	X
Usage of rescue medication	Х	X	Х	X	X	X	Х	X	Х	Х	Х	X	Х
AEs	X	X	X	X	X	X	X	X	X	X	X	X	X

All patients in the pilot phase will titrate GWP42003-P in an inpatient setting. In both phases (pilot and pivotal), daily safety checks will be made during the first week of IMP dosing (can be conducted by telephone). Each safety check will conduct the same assessments as listed for safety follow-up visit.

²Daily safety checks will be made during the first week of OLE IMP dosing (can be conducted by telephone). Each safety check will conduct the same assessments as listed for safety follow-up visit.

³IMP is to be tapered over 10 days following discontinuation of IMP, end of treatment, or withdrawal (unless continued dosing is not possible due to an AE).

⁴Safety follow-up visit is to occur 28 (+3) days after date of final dose (including tapered dose); weekly (±3 days) telephone calls must be made during the follow-up period. Each safety telephone call will conduct the same assessments as listed for safety follow-up visit.

⁵Based on assessment of clinical laboratory and video-EEG results.

 $^{^6\}mathrm{ECG}$ to be performed between 3 and 5 hours after the day's first dose of IMP only.

⁷ECG to be performed both prior to the day's first dose of IMP and between 3 and 5 hours after this dose.

⁸Only for patients involved in the pivotal phase, and progressing to the OLE from the pivotal phase. To be conducted only if the risk/benefit outcome is favorable, in the investigator's opinion.

⁹Memory aid only (worksheet completed).

¹⁰If necessary, IMP will also be dispensed for taper period.

¹¹IMP usage to be recorded on a dosing schedule which will form part of the paper diary

2.5. Primary Endpoints

The following endpoints will be analyzed descriptively only:

2.5.1. Pilot Phase

- Safety as determined by AEs, clinical laboratory tests, ECG, vital signs and physical examinations during the treatment period
- The number and proportion of patients who are free of spasms and have resolution of hypsarrhythmia at the end of the 2-week treatment period, as determined by video-EEG.

2.5.2. *OLE Phase*

• To assess the long term safety as determined by AEs, clinical laboratory tests, ECG, vital signs and physical examinations during the treatment period.

2.6. Secondary Endpoints

2.6.1. *Pilot Phase*

For the pilot phase, the following secondary endpoints will be analyzed descriptively only:

- The number and proportion of patients who are free of clinical spasms, as observed on video-EEG at the end of the treatment period.
- The number and proportion of patients who have resolution of hypsarrhythmia, as observed on video-EEG at the end of the treatment period.
- Changes in spasms and seizure subtypes by caregiver observation during the treatment period.
- Time to cessation of spasms during the treatment period, as determined by caregiver diaries.
- CGIC.
- PGIC.

2.6.2. *OLE Phase*

For the OLE phase, the following secondary endpoints will be analyzed descriptively only:

- The number and proportion of patients who are free of clinical spasms, as observed on video-EEG at the end of the treatment period.
- The number and proportion of patients who have resolution of hypsarrhythmia as, observed on video-EEG at the end of the treatment period.
- Changes in spasms and seizure subtypes by caregiver observation during the treatment period.
- Time to cessation of spasms during the treatment period, as determined by caregiver diaries.
- The number and proportion of patients who are free of spasms and have resolution of hypsarrhythmia, as determined by video-EEG after 3, 6, 9 and 12 months of treatment.

GW Research Ltd Study Code: GWEP15100 EudraCT Number: 2015-004904-50

25SEP2019

- The number and proportion of responders with relapse of spasms, and the time to relapse, as determined by caregiver diaries.
- Changes from baseline in length (height), body weight, and head circumference.
- CGIC.
- PGIC.
- Change from baseline in Vineland-II score.

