3.2 GWP42003-P Background

The investigational medicinal product (IMP), GWP42003-P, is formulated from extracts prepared from *Cannabis sativa* L. plants that have a defined chemical profile and contain consistent levels of CBD as the principal phytocannabinoid. Extracts from these plants are processed to yield purified (\geq 98%) CBD that typically contains less than 0.15% (w/w) Δ^9 -tetrahydrocannabinol (THC). The purified CBD is subsequently dissolved in excipients with added sweetener and flavoring.

The pharmacological effects of phytocannabinoids are thought to be mediated primarily via their interaction with the endocannabinoid system, which comprises cannabinoid receptors, endogenous ligands (endocannabinoids), and enzymes for endocannabinoid synthesis and degradation. To date, 2 G-protein-coupled receptors for cannabinoids have been identified, designated CB₁ receptor and CB₂ receptor. CBD does not bind to either of these receptors with any great affinity but does modulate the metabolizing enzymes of the endocannabinoid system. CBD also affects conduction of ion channels and acts on other G-protein-coupled receptors such as the transient receptor potential channel TRPV1⁴² and the orphan receptor GPR55⁴³. Importantly, CBD lacks the psychoactivity associated with THC. Further to this, CBD has demonstrated anticonvulsant, antipsychotic, anxiolytic, neuroprotective, antioxidant and anti-inflammatory activity ⁴⁴. Data concerning adverse events (AEs) of CBD in humans are limited; however, in the small number of placebo-controlled trials published to date investigating the anticonvulsant effects of CBD, few side

EudraCT Number: 2015-004904-50

Protocol V3 20Sep16

effects have been reported after 4–12 months of 200–300 mg/day CBD⁴⁴. A recent abstract at the American Epilepsy Society 2015 Annual Meeting described the safety profile of GWP42003-P (up to 25 mg/kg/day) in 313 adults and children in a compassionate use program in the US⁴⁵. The most common AEs (i.e., reported in \geq 10% of patients) were somnolence (23%), diarrhea (23%), fatigue (17%), decreased appetite (17%), convulsions (17%), and vomiting (10%). Dropouts due to AEs were 4%.

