1.2.2.2. Secondary Objectives

- **Key:** To assess the number and proportion of patients who are free of clinical spasms, as observed on video-electroencephalography (video-EEG) at the end of the treatment period.
- **Key:** To assess the number and proportion of patients who have resolution of hypsarrhythmia, as observed on video-EEG at the end of the treatment period.
- To assess changes in spasms and seizure subtypes by caregiver observation during the treatment period.
- To determine time to cessation of spasms during the treatment period, as determined by caregiver diaries.
- To explore the effect of GWP42003-P on quality of life.
- To assess the number and proportion of patients who are free of spasms and have resolution of hypsarrhythmia, after 3, 6, 9 and 12 months of treatment.
- To assess the number and proportion of responders who relapse and the time to relapse.
- To explore the effect of GWP42003-P on growth, adaptive behavior and development.
- To determine the population POPPK of CBD and its metabolites (6-OH-CBD, 7-COOH-CBD and 7-OH-CBD)

GW Research Ltd Study Code: GWEP15100 EudraCT Number: 2015-004904-50 25SEP2019

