4.2.9. Baseline Definition

Unless otherwise noted, baseline (for both the pilot and OLE phases) is defined as the data most recently collected prior to the first IMP dosing start date/time in the pilot phase. If the timing of some data collection is not recorded, it will be assumed that the assessment at the first dosing date is performed as planned, i.e. prior to dosing in the pilot phase.

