4.8.4. Vital Signs and Physical Examinations

Vital signs measurements (systolic and diastolic blood pressure, pulse rate, body temperature, respiratory rate, height, weight, BMI, and head circumference), taken in a supine position at rest for 5 minutes, will be completed alongside the physical examination.

Physical examinations will include length (height), body weight, and head circumference measurements.

Vital signs and physical examination data will be summarized at screening, baseline, and at each time point during the treatment period using descriptive statistics. Changes in the vital signs from baseline to end of treatment will also be summarized.

All vital sign and physical examination measurements will be presented in data listings.

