- Table 11.5.2 Treatment-Emergent Adverse Events by System Organ Class and Preferred Term and Sex OLE Phase Safety

GW Research Ltd Study Code: GWEP15100 EudraCT Number: 2015-004904-50 25SEP2019

- Table 11.6.1: Non-Serious Treatment Emergent Adverse Events by System Organ Class and Preferred Term for Subjects and Events Pilot Phase Safety
- Table 11.6.2: Non-Serious Treatment Emergent Adverse Events by System Organ Class and Preferred Term for Subjects and Events OLE Phase Safety
- Table 12.1.1 Serious Treatment-Emergent Adverse Events by System Organ Class and Preferred Term Pilot Phase Safety
- Table 12.1.2 Serious Treatment-Emergent Adverse Events by System Organ Class and Preferred Term OLE Phase Safety
- Table 12.2.1 Treatment Related Serious Treatment-Emergent Adverse Events by System Organ Class and Preferred Term Pilot Phase Safety
- Table 12.2.2 Treatment Related Serious Treatment-Emergent Adverse Events by System Organ Class and Preferred Term OLE Phase Safety
- Table 12.3.1 Treatment-Emergent Adverse Events Leading to Study Drug Discontinuation by System Organ Class and Preferred Term Pilot Phase Safety
- Table 12.3.2 Treatment-Emergent Adverse Events Leading to Study Drug Discontinuation by System Organ Class and Preferred Term OLE Phase Safety
- Table 12.4.1 Treatment Related Treatment-Emergent Adverse Events Leading to Study Drug
- Discontinuation by System Organ Class and Preferred Term Pilot Phase Safety
- Table 12.4.2 Treatment Related Treatment-Emergent Adverse Events Leading to Study Drug Discontinuation by System Organ Class and Preferred Term OLE Phase Safety
- Table 12.5.1 Fatal Treatment-Emergent Adverse Events by System Organ Class and Preferred Term Pilot Phase Safety
- Table 12.5.2 Fatal Treatment-Emergent Adverse Events by System Organ Class and Preferred Term OLE Phase Safety
- Table 13.1.1 Summary of Laboratory Test Results and Change from Baseline by Visit Hematology Pilot and OLE Phase Safety
- Table 13.1.2 Summary of Laboratory Test Results and Change from Baseline by Visit Chemistry Pilot and OLE Phase Safety
- Table 14.1 Summary of Vital Signs Results and Change from Baseline by Visit Pilot and OLE Phase Safety
- Table 14.2 Summary of Physical Examination Results and Change from Baseline by Visit Pilot and OLE Phase Safety
- Table 14.3.2 Summary of ECG Results and Change from Baseline by Visit Pilot and OLE Phase Safety
- Table 13.2.1 Hematology Shift Table Based on Reference Ranges Pilot and OLE Phase Safety

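### Growth in the extension is planned as unstandardised change from baseline, a summary that cannot separate normal from slowed growth in infants

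*SAP*

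**What the plan says.** SAP 1.2.2.2 sets the extension objective "To explore the effect of GWP42003-P on growth, adaptive behavior and development". SAP 2.6.2 serves the growth part with "Changes from baseline in length (height), body weight, and head circumference", as do protocol 4.1.2.3 and 13.6.3.3.

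SAP 4.7 has no growth subsection. The measurements are handled in SAP 4.8.4, where "Physical examinations will include length (height), body weight, and head circumference measurements". That section also names BMI, and it asks for descriptive statistics at each time point. The output is "Table 14.2 Summary of Physical Examination Results and Change from Baseline by Visit Pilot and OLE Phase Safety". Individual values go into Listing 14.1.

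Entrants are "the first cohort aged between 6 and 24 months and the second cohort aged between 1 and 24 months" (SAP 2.1), and the last extension visit is Day 379. Under SAP 4.2.9, "baseline (for both the pilot and OLE phases) is defined as the data most recently collected prior to the first IMP dosing start" date and time in the pilot phase, so change at the last visit spans the whole follow-up. There is one open-label treatment column (SAP 4.2.1), no covariate adjustment (4.2.4) and no subgroup analysis (4.2.6). The pivotal phase, which had the placebo arm, is omitted (SAP 5).

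Neither document mentions z-scores, centiles, growth velocity, a growth reference, or a criterion for slowed growth.

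**The concern.** Over a year an infant gains length, weight and head circumference. Without a control arm, a change from baseline means something only against what would be expected at that age and sex, and the plan supplies no such expectation. An infant growing too slowly still contributes a positive change, and the same gain can be ample for an older entrant and poor for a younger one.

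Poor growth is a foreseeable question for this drug. Protocol 3.2 reports diarrhea in 23%, decreased appetite in 17% and vomiting in 10% of 313 compassionate-use patients. Those were adults and children, so the rates do not carry over to infants, but they are reason to want a growth summary that can be interpreted. The measurements also belong to the physical examinations that form part of the extension's primary safety endpoint (SAP 2.5.2).

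**Working it through.** The plan states no figure for this endpoint, so there is none to reproduce.

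**1. Span of the change.** Day 379 − Day 1 = 378 days; 378 / 30.44 = 12.4 months.

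**2. Sign.** Let G be the expected gain over follow-up and f the fraction of it lost. Raw change = G(1 − f). With G > 0 this is positive for every f below 1. This step needs no outside figure.

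**3. Size, by illustration.** The documents give no growth values, so every kilogram figure here is an assumption, and only weight is illustrated. Suppose 12-month gain falls linearly from g1 (entry at 1 month) to g24 (entry at 24 months), with entry age uniform over 1-24 months. The mean raw change is (g1 + g24)/2 × (1 − f):

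| Assumed gain, youngest to oldest entrant | f = 0 | f = 0.25 | f = 0.5 | f = 0.75 |
|---|---|---|---|---|
| 4 to 1.5 kg | +2.75 | +2.06 | +1.38 | +0.69 |
| 6 to 2 kg | +4.00 | +3.00 | +2.00 | +1.00 |
| 7 to 3 kg | +5.00 | +3.75 | +2.50 | +1.25 |

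In 20,000 simulated groups of nine (the pilot number in SAP 4.1), with an assumed residual SD of 0.5 kg, the group mean was positive in about 99.99% of groups or more in every cell.

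**4. Overlap.** In the middle row, the central 95% of nine-infant means is 3.2 to 4.8 kg with normal growth and 2.4 to 3.7 kg with a quarter of growth lost. Most of that spread comes from entry age: the SD of G is (6 − 2)/√12 = 1.15 kg, against 0.5 kg residual. A half loss does not overlap with normal growth within that row (1.5 to 2.5 kg), but seeing this requires knowing which row applies, and the plan names no reference. Normal growth in the first row (+2.75 kg) is close to half of all growth lost in the third (+2.50 kg).

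**5. Entry age.** In the middle row, G at age a is 6 − 4(a − 1)/23. At a mean entry age of 18 months, G = 6 − 68/23 = 3.04 kg. At 6 months, G = 6 − 20/23 = 5.13 kg. The younger group records the same +3.04 kg after losing 1 − 3.04/5.13 = 41% of its growth.

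**6. What the minimum would show.** If a share s of infants has a negative 12-month weight change, the chance that at least one of nine does is 1 − (1 − s)^9.
- First row: s = 0.012 at f = 0.5 gives 10%; s = 0.097 at f = 0.75 gives 60%.
- Middle row: s = 0.002 gives about 2%; s = 0.042 gives 32%.

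So the minimum has some chance of showing a severe deficit and little chance of showing a moderate one.

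**The case against.** The strongest reply is that with about nine infants little is hidden. SAP 4.2.1 requires minimum and maximum, Table 14.2 runs by visit, and all measurements are listed. Weight loss or a plateau in one infant would be visible, and BMI can fall while weight and length both rise. An investigator can also report poor growth as an adverse event. The objective is exploratory, and no test is planned.

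Most of this stands, and it limits the point. A reader might infer that growth faltering cannot be detected at all. The documents do not support that: the limit lies in the planned summary, and the listed data would allow standardisation later, although none is planned. A reader might also infer that a positive change will be presented as benefit. Nothing in either document says so.

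The reply does not rescue the summary itself. BMI is unstandardised too, and it can miss slowing that affects weight and length together or slow head growth. A slowed but still positive gain does not stand out in a minimum or a listing without an age reference. A descriptive statistic should still describe the quantity named in the objective.

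**Conclusion.** The point holds for the planned summary. Mean change in length, weight and head circumference will be positive under ordinary growth and under substantially slowed growth, and its size depends largely on entry age. The sign argument rests only on expected growth being positive. The magnitudes (+1.38 to +2.50 kg with half of growth lost) rest on assumed gains, a 0.5 kg residual SD, and uniform entry ages over 1-24 months. Cohort 1 actually starts at 6 months, actual ages are not given, and the number entering or completing the extension is not stated.

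No type I error, power or hypothesis test is affected. The consequence is that a stated objective cannot be addressed by its planned table. It would also be too strong to infer that standardising would isolate the drug's effect. Protocol 3.1 ties infantile spasms to Down syndrome, tuberous sclerosis, brain malformations and perinatal injury, and underlying disease can move z-scores as well. In a small uncontrolled group, z-scores can indicate whether growth slowed but not why.

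**What to change.** In SAP 4.8.4 and Table 14.2:

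- Add age- and sex-standardised z-scores for length, weight and head circumference at each visit, from one named infant growth reference, with age corrected for gestational age at birth where available.
- Report change in z-score from baseline and the number of infants whose z-score falls by a pre-stated amount.
- Keep the raw values in Listing 14.1.
- Base any growth statement on the z-scores.

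The cost is SAP wording and derived variables. Date of birth, sex and gestational age are collected under protocol 9.2.3, and the measurements recur at Visits 1, 2, 4, 6-12 and the end of taper. The downsides are that a reference and a threshold must be chosen, and the documents supply neither. Exact age or gestational age may also be missing where local rules limit collection; the SAP should say how those infants are handled. The report should state that the result is descriptive and does not establish a drug effect.
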